4.7. Interim Analyses

An early interim analysis may be conducted at the discretion of Alexion (based on feasibility) when approximately 50% of participants in the IgAN and/or LN disease-specific cohorts have been randomly assigned to study treatment and have had the opportunity to complete the 26-week Blinded Initial Evaluation Period or have discontinued from the study treatment before Week 26. This early interim analysis, if performed for either the IgAN cohort and/or the LN cohort, will be conducted by a separate unblinded team and will be for Phase 3 planning purposes only, including any applicable regulatory interactions, with no impact on the progression of the study.

The primary efficacy analysis will be performed for each disease-specific cohort at the end of the 26-week Blinded Initial Evaluation Period after all participants in the disease-specific cohort have completed or withdrawn from the 26-week Blinded Initial Evaluation Period.

An additional analysis will be performed for each disease-specific cohort at the end of the 24-week Blinded Extended Treatment Period after all participants in the disease-specific cohort have completed the Week 50 Visit or withdrawn from the study early. This additional analysis will include all planned efficacy, PK/PD, and safety analyses.

The final analysis will be performed at the end of the 2-year OLE Period after all participants have completed the Safety Follow-up Visit and will include all planned analyses that will be presented in the final clinical study report.

4.8. Changes to Protocol-planned Analyses

Based on actual data received from laboratory, the RBC in urine is categorical data. Hence, the endpoint of hematuria will be analyzed as categorical variable instead of continuous variable.

5. SAMPLE SIZE DETERMINATION

This study plans to enroll approximately 126 adult participants with either LN or IgAN in the study (approximately 70 participants in the LN cohort and approximately 56 participants in the IgAN cohort) in a 3:1:3 ratio to ALXN2050 180 mg bid, ALXN2050 120 mg bid, or placebo. All participants will receive standard of care treatment in addition to their randomized treatment.

The primary analysis of the primary endpoint will test the hypothesis that ALXN2050 180 mg bid is superior to placebo in decreasing proteinuria. Data from the ALXN2050 120 mg bid treatment group will be summarized descriptively, with no formal statistical testing planned.

In Mar 2018, an NKF-sponsored workshop on surrogate endpoints for clinical studies in early stages of chronic kidney disease was held. A 20% to 30% reduction in the geometric mean of albuminuria or proteinuria was decided as a clinically significant treatment effect (Levey, 2020). Sample size calculations are based on a 1-sided 2-sample t-test of log-transformed proteinuria values.

Individual participant data from relevant studies in IgAN was previously used to estimate variability and expected changes in proteinuria for participants on placebo with background standard of care treatment (Fellström, 2017). Based on this data, the geometric mean (GM) of the ratio of 26-week to baseline proteinuria values is assumed to be 0.85 (ie, a 15% reduction from baseline in proteinuria) for the placebo group. In order to target at least a 30% relative treatment effect, (ie, 1 minus GMR of ALXN2050 180 mg bid to placebo at Week 26), the GM of the ratio of 26-week to baseline is assumed to be 0.55 (ie, a 45% reduction from baseline in proteinuria) for the ALXN2050 180 mg bid group. The log change from baseline in proteinuria is calculated as log (0.85) and log (0.55) for the placebo and ALXN2050 180 mg bid treatment groups, respectively, for the IgAN cohort. A common SD of log change is assumed to be 0.60 (Fellström, 2017). Under these assumptions and an anticipated 10% drop out rate, a sample size of 48 participants (24 participants randomized to ALXN2050 180 mg bid, 24 participants randomized to placebo) in the IgAN cohort will provide approximately 80% power to detect a treatment difference with a 1-sided significance level of 0.05. An additional 8 participants will be enrolled in the ALXN2050 120 mg bid treatment group for a total of 56 participants in the IgAN cohort.

Expected changes in proteinuria and associated variability were not available on the log-scale for LN; however, 2 studies of participants with LN who were treated with mycophenolate mofetil (MMF) showed mean proteinuria values of approximately 4 g/day at baseline and approximately 2 g/day at Week 24 (Appel, 2009; Ginzler, 2005). The GM of the ratio of 26-week to baseline proteinuria values is assumed to be 0.60 (ie, a 40% reduction from baseline in proteinuria) for the placebo group. In order to target at least a 30% relative treatment effect (ie, 1 minus GMR of ALXN2050 180 mg bid to placebo at Week 26), the GM of ratio of 26-week to baseline is assumed to be 0.40 (ie, a 60% reduction from baseline in proteinuria) for the ALXN2050 180 mg bid group. The log change from baseline in proteinuria is calculated as log (0.60) and log (0.40) for the placebo and ALXN2050 180 mg bid treatment groups, respectively, for the LN cohort. A common SD of log change is assumed to be 0.60 (Fellström, 2017). Under these assumptions and an anticipated 10% drop out rate, a sample size of 60 participants (30 participants randomized to ALXN2050 180 mg bid, 30 participants randomized to placebo) in the LN cohort will provide approximately 80% power to detect a treatment difference with a 1-sided significance level of

0.05. An additional 10 participants will be enrolled in the ALXN2050 120 mg bid treatment group for a total of 70 participants in the LN cohort.

6. SUPPORTING DOCUMENTATION

6.1. Technical Specifications for Derived Variables

The following derived data will be calculated prior to analysis.

6.1.1. Disease Duration

Disease duration will be presented as the number of years between date of first dose and date of diagnosis as reported on the Medical History eCRF. Missing dates will be handled as described in Section 4.1.4.

6.1.2. Definition of Baseline Values

For the 26-week Blinded Initial Evaluation Period, baseline is defined as the last available assessment value prior to the first dose of study intervention. For the 24-week Blinded Extended Treatment Period, a re-baseline is defined as the last available assessment prior to the first dose of study intervention administered in the extension period.

6.1.3. Change from Baseline

Change from baseline will be calculated as the baseline value subtracted from the value at a particular time point. If one of the values is missing and there are no prespecified missing value imputation rules (see Section 4.1.4), then a change from baseline will not be calculated.

6.1.4. Percent Change from Baseline

Percent change from baseline will be calculated as (change from baseline / baseline value) × 100%. If one of the values is missing and there are no prespecified missing value imputation rules (see Section 4.1.4) or if the baseline value is zero, then a percentage change from baseline will not be calculated.

6.1.5. Analysis Visits

Summaries over post-Baseline time points or analyses at specific post-Baseline time points will be performed based on the list of visits described in the schedule of assessment of the protocol. For all assessments, the number of days from baseline will be calculated using the following formula: (date of assessment) – (date of first study treatment) + 1. Relative days prior to Day 1 are calculated as (date of assessment – date of Day 1 Visit). This number of days will be used to assign analysis visit.

The analysis visit assignment for a specific assessment will be based on visit windows around each scheduled visit for that specific assessment. The windows for each scheduled visit will go from the midpoint (in days) between the current visit and the previous scheduled visit to the midpoint between the current visit and the subsequent scheduled visit. If the interval separating 2 scheduled visits is an even number of days, that middle day will be included in the later visit window and excluded from the prior visit window. For example, for an assessment with a scheduled visit Day 127, and a prior scheduled visit Day of 113 and subsequent scheduled visit Day of 141, the window will start at 120 days from baseline and will go to 133 days from baseline.

6.1.6. Analysis Value

The values being considered for analysis at a specific post-Baseline time point will be based on the analysis visit assigned to that value. If there is more than 1 nonmissing value for a specific assessment with the same analysis visit, the value used for analysis will be the one for which the calculated number of days from baseline is closest to the scheduled visit day. If 2 values have the same analysis visit and are the same distance away from the scheduled visit day, the earlier of the 2 values will be used for analysis.

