8.1.2. Spot Urine Sample (Both Cohorts)

Urinary protein, albumin, and creatinine levels from morning spot urine samples prior to dosing will be measured at the time points specified in the SoA (Section 1.3) to assess the effect of study intervention on UPCR and UACR.

Two consecutive spot urine samples will be obtained for participants in both disease cohorts at Week 16 for the LN cohort and at Week 18 for the IgAN cohort.

The UPCR and UACR results will be recorded in the participant's eCRF.

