8.1.3. Estimated Glomerular Filtration Rate (Both Cohorts)

Changes in renal function will be monitored using measurements of eGFR (mL/min/1.73 m²) and creatinine clearance on a 24-hour urine collection. Serum creatinine will be analyzed as part of the clinical chemistry (Section 10.2) collected predose. The eGFR calculation will be based on the CKD-EPI formula.

For the determination of CRR and PRR in the LN Cohort at Week 26 and Week 50, 2 serum creatinine samples for eGFR will be obtained, the first within 2 weeks prior to each of these study visits and the second on the study visit day. The blood sample collection could occur at the participant's home if agreed upon with the Investigator and the participant. The collection will be recorded in the eCRF according to the eCRF completion guidelines.

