4.3.1.4. Complete Renal Response (LN Cohort Only)

Complete renal response (CRR) will be assessed at Weeks 26 and 50. To achieve CRR, participants in the LN cohort must meet all of the following criteria:

- A decrease in mean UPCR to ≤ 0.5 g/g based on two 24-hour urine collections obtained within 2 weeks prior to the study visit (Week 26 or 50)
- eGFR > 60 mL/min/1.73 m² or no eGFR reduction ≥ 20% from the baseline value based on the mean of 2 values. The first eGFR value must be obtained within 2 weeks prior to the study visit (Week 26 or 50) and the second eGFR value will be obtained on the study visit (Week 26 or 50)
- No treatment failure (as defined in Section 4.3.1.10)

The percentage of participants meeting the criteria for CRR as well as individual components of CRR will be summarized at Weeks 26 and 50 by treatment group by calculating the point estimate and 2-sided 95% CI, based on exact confidence limits using the Clopper-Pearson method.

Study participants with treatment discontinuation will be treated as failure to meet CRR criteria and considered nonresponders.

A bar chart will also be provided displaying the proportion of participants meeting the criteria for CRR as well as individual components of CRR at Weeks 26 and 50 by treatment group.

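### SAP 6.1.6 uses one of two scheduled replicates for LN eGFR change (Weeks 26 and 50) and by-visit spot UPCR (Week 16/18), costing some precision and giving LN participants two eGFR values for one visit

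*SAP*

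**What the plan says.** **General rule.** SAP 6.1.5 builds analysis windows from the midpoints between scheduled visits. Where several values land in one window, SAP 6.1.6 selects "the one for which the calculated number of days from baseline is closest to the scheduled visit day"; if two are equally distant, "the earlier of the 2 values will be used for analysis". It has no clause for samples that the protocol deliberately takes in pairs.

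**Scheduled pairs.** Protocol 8.1.3 provides that "2 serum creatinine samples for eGFR will be obtained, the first within 2 weeks prior to each of these study visits". The other creatinine is drawn at the visit itself. The stated purpose is to decide CRR and PRR in LN participants at Weeks 26 and 50. For urine, Protocol 8.1.2 says "Two consecutive spot urine samples will be obtained for participants in both disease cohorts". The LN pair belongs to the Week 16 visit and the IgAN pair to the Week 18 visit.

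**Where the SAP averages instead.** The 24-hour urine collections are averaged (SAP 4.2.1 and the CRR, PRR and partial remission criteria). The eGFR component of CRR and PRR is "based on the mean of 2 values" (SAP 4.3.1.4 and 4.3.1.5, repeated in 6.1.8 and 6.1.11). IgAN baseline eGFR is the mean of Screening and Day 1 (SAP 4.3.1.3).

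**Where it does not.** SAP 4.3.1.3 (post-baseline eGFR change) and the spot UPCR model in SAP 4.3.1.1 say nothing about combining replicates, so 6.1.6 applies to both.

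**The concern.** Change in eGFR is listed among the key secondary variables (SAP Table 6). At LN Weeks 26 and 50 its value comes from one creatinine, while the CRR and PRR eGFR component, reported for the same participants and visit, comes from two. An LN participant with eGFR at or below 60 mL/min/1.73 m² could meet that component on the mean of two values and still show a fall of 20% or more in the change-from-baseline data. The SAP does not mention this or say which value represents the visit.

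The second issue is precision. These samples are collected anyway, and a mean of two is less variable than one value whenever the replicates are not perfectly correlated. For spot urine, no section says how the pair is combined. Distance is counted in days, so two samples on one date would tie, and the rule does not say whether clock time decides which is earlier.

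**Working it through.** **1. Reproduce the SAP's own window.** For a visit on Day 127 with neighbours on Days 113 and 141, the midpoints are (113+127)/2 = 120 and (127+141)/2 = 134. An exact middle day goes to the later visit, so the window is Days 120 to 133. SAP 6.1.5 says the same: "the window will start at 120 days from baseline and will go to 133 days from baseline".

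**2. Apply the rule to the paired samples** (scheduled days from Protocol Tables 1 to 5).

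| Assessment | Scheduled days (previous, current, next) | Window |
|---|---|---|
| LN Week 26 eGFR | 141, 183, 239 | 162 to 210 |
| LN Week 50 eGFR | 295, 351, 442 | 323 to 396 |
| LN Week 16 spot urine | 85, 113, 141 | 99 to 126 |
| IgAN Week 18 spot urine | 85, 127, 183 | 106 to 154 |

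**3. Do both creatinines share a window?** The visit tolerance is ±5 days at Week 26 and ±7 days at Week 50, and the first sample comes 1 to 14 days before the visit.

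- Week 26: earliest first sample is Day 183 − 5 − 14 = 164, inside 162 to 210. Latest visit is Day 188, also inside.
- Week 50: earliest first sample is Day 351 − 7 − 14 = 330, inside 323 to 396. Latest visit is Day 358, also inside.

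All 11 × 14 = 154 day combinations at Week 26 and all 15 × 14 = 210 at Week 50 put both samples in one window. When both are collected on schedule, one is always set aside.

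Consecutive spot samples around Day 113 ± 5 or Day 127 ± 5 also share their window.

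**4. Which creatinine is dropped?** If the visit is on or before its scheduled day, the pre-visit sample is further away and is dropped. If the visit is late, the pre-visit sample can be closer.

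- Week 26: pre-visit sample strictly closer in 25 combinations, tied in 5. The visit-day sample is dropped in 30 of 154, the pre-visit sample in 124.
- Week 50: strictly closer in 49, tied in 7. The visit-day sample is dropped in 56 of 210, the pre-visit sample in 154.

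These are counts of calendar possibilities, not forecast frequencies.

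**5. Precision.** For two replicates with equal variance and correlation ρ, Var(mean of 2)/Var(single) = (1 + ρ)/2, so the SE ratio is √((1 + ρ)/2). For a change score in which within-person noise in the post-baseline value makes up a share f of the variance, and replicate errors are independent, the SE ratio is √(1 − f/2). The documents give neither ρ nor f; both are assumed.

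| ρ | f | SE ratio | Reduction in SE |
|---|---|---|---|
| 0.95 | 0.05 | 0.987 | 1.3% |
| 0.9 | 0.1 | 0.975 | 2.5% |
| 0.8 | 0.2 | 0.949 | 5.1% |
| 0.7 | 0.3 | 0.922 | 7.8% |
| 0.5 | 0.5 | 0.866 | 13.4% |

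As an eGFR illustration, assume a within-person SD of 4 to 6 mL/min/1.73 m² and an SD of change of 15. The variance falls by (16/2)/225 = 3.6% to (36/2)/225 = 8%, so the SE falls by 1 − √0.964 = 1.8% to 1 − √0.92 = 4.1%.

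**The case against.** A closest-to-visit rule with a tie-break is clear, prespecified and conventional. A responder definition may reasonably specify its own eGFR value. The first creatinine can precede the visit by up to 14 days, so it is not a same-time replicate, and averaging centres the value up to 14/2 = 7 days before the visit day. LN baseline eGFR is the lowest pre-dose value (SAP 4.3.1.3), and averaging after baseline does nothing about that. All of this stands. It makes the point an improvement rather than the correction of an error. The earlier centring is already accepted for CRR and PRR.

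Three stronger readings are tempting, and the documents do not support them.

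- *That the visit-day creatinine is thrown away, or that a creatinine is lost to the trial.* The sample usually dropped is the pre-visit one. Both are used, as a mean, for CRR and PRR, which is the purpose stated in Protocol 8.1.3.
- *That no analysis uses the second spot urine.* SAP 6.1.6 governs values at a specific time point. The first-occurrence analyses (time to UPCR ≤ 0.5 g/g, 4.3.1.6; time to first CRR or PRR, 4.4.7; time to a > 50% decrease, 4.4.9) do not clearly limit events to one sample per window. The point holds for the by-visit model only.
- *That a definite loss can be quoted.* There is no replicate variance in either document. The SAP's 0.60 SD is the planning value for log change in the primary 24-hour endpoint, so using it for spot UPCR would be borrowing. Samples taken close together may also share short-term variation, which would shrink the gain.

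**Conclusion.** The point holds as a minor one. Under SAP 6.1.6, LN eGFR change at Weeks 26 and 50 rests on one of two scheduled creatinines, and the by-visit spot UPCR model rests on one of two samples at Week 16 or 18. The direction of the precision loss is certain for replicates of equal variance correlated below 1. Its size is about 1% to 13% of the SE at those visits only, and depends wholly on the assumed ρ or f.

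The inconsistency between the eGFR change value and the CRR/PRR value needs no variance assumption and is the firmer half.

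The consequences are limited. Secondary analyses are descriptive (SAP 4.3), no formal comparison is planned for eGFR (SAP 4.3.1.3), and the spot UPCR model is an addition to the 24-hour analysis. The primary endpoint, its power, the other 24-hour measures and post-baseline IgAN eGFR are untouched.

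**What to change.** Add to SAP 6.1.6: where the protocol schedules two samples for one visit (LN creatinine at Weeks 26 and 50; spot urine at Week 16 for LN and Week 18 for IgAN), the analysis value for by-visit analyses is the mean of the two; if only one is available, that value is used. For eGFR, average the two eGFR values, as CRR and PRR do. For UPCR, average first and log-transform afterwards, as SAP 4.2.1 does for 24-hour urine, so that the SAP keeps a single averaging convention.

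Limiting the sentence to by-visit analyses leaves the first-occurrence endpoints as they are.

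The cost is one sentence and a small programming change, with no new data. The trade-off is an eGFR value centred up to about one week before the visit day. The sentence should be in place before the sponsor is unblinded for the Week 26 analysis, so that the choice cannot follow the results.

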6.1.7. Adverse Events

The analysis of AEs is described in detail in Section 4.5.2.

Treatment-emergent AEs (TEAEs) are events with start dates and start times on or after the date and time of the first dose of study intervention and up to 30 days after the last dose of study intervention. If the start date of an AE is partially or completely missing and the end (stop) date and time of the AE does not indicate that it occurred prior to first dose or 30 days after the last dose, then the determination of treatment-emergent status will be based on the following:

- If the start year is after the year of the first dose of study intervention and before the year of the last dose of study intervention, then the AE is treatment-emergent; else
- If the start year is the same as the year of the first dose of study intervention and
 - the start month is missing, then the AE is treatment-emergent; else, if
 - the start month is present and is the same or after the month of the first dose of study intervention and is the same or before the last dose of study intervention, then the AE is treatment-emergent; else,
- If the start date is completely missing, then the AE is treatment-emergent.

All other AEs are considered pretreatment adverse events (PTAEs) if the start date is prior to the first dose of study intervention or post-treatment adverse events if the start date is 30 days or later after the last dose of study intervention.

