10.3.1. Definition of AE

AE Definition

- An AE is any untoward medical occurrence in a participant or clinical investigation participant
 administered a pharmaceutical product and which does not necessarily have to have a causal
 relationship with this treatment (ICH E2A).
- Note: An AE can therefore be any unfavorable and unintended sign (including an abnormal laboratory finding), symptom, or disease [new or exacerbated] temporally associated with the use of the study intervention, whether or not considered related to the study intervention.

Events Meeting the AE Definition

- Any abnormal laboratory test results (hematology, clinical chemistry, or urinalysis) or other safety
 assessments (eg, ECG, radiological scans, vital signs measurements), including those that worsen
 from baseline, considered clinically significant in the medical and scientific judgment of the
 Investigator (ie, not related to progression of underlying disease).
- Exacerbation of a chronic or intermittent pre-existing condition including either an increase in frequency and/or intensity of the condition.
- New conditions detected or diagnosed after study intervention administration even though it may
 have been present before the start of the study.
- Signs, symptoms, or the clinical sequelae of a suspected drug-drug interaction.
- Signs, symptoms, or the clinical sequelae of a suspected overdose of either study intervention or a
 concomitant medication. Overdose per se will not be reported as an AE/SAE unless it is an
 intentional overdose taken with possible suicidal/self-harming intent. Such overdoses should be
 reported regardless of sequelae.

Events Not Meeting the AE Definition

- Medical or surgical procedure (eg, endoscopy, appendectomy): The condition that leads to the
 procedure is the AE. Situations in which an untoward medical occurrence did not occur (eg,
 hospitalization for elective surgery if planned before signing the ICF, admissions for social reasons
 or for convenience).
- Anticipated day-to-day fluctuations of pre-existing disease(s) or condition(s) present or detected at the start of the study that do not worsen.
- A medication error (including intentional misuse, abuse, and overdose of the product) or use other
 than what is defined in the protocol is not considered an AE unless there is an untoward medical
 occurrence as a result of a medication error.

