 - The event does not follow a reasonable temporal relationship to administration of the study intervention.
 - Related: There is a reasonable possibility the study intervention caused the AE.
 - The AE has a temporal relationship to the administration of the study intervention.
 - The event does not have a likely alternative etiology.
 - The event corresponds with the known pharmaceutical profile of the study intervention.
 - There is improvement on discontinuation and/or reappearance on rechallenge.
- The Investigator will use clinical judgment to determine the relationship.
- Alternative causes, such as underlying disease(s), concomitant therapy, and other risk factors, as
 well as the temporal relationship of the event to study intervention administration will be
 considered and investigated.
- The Investigator will also consult the IB and/or Product Information, for marketed products, in his/her assessment.
- For each AE/SAE, the Investigator must document in the medical notes that he/she has reviewed
 the AE/SAE and has provided an assessment of causality.
- There may be situations in which an SAE has occurred, and the Investigator has minimal
 information to include in the initial report to Alexion. However, it is very important that the
 Investigator always make an assessment of causality for every event before the initial transmission
 of the SAE data to Alexion.
- The Investigator may change his/her opinion of causality in light of follow-up information and send an SAE follow-up report with the updated causality assessment.
- The causality assessment is one of the criteria used when determining regulatory reporting requirements.

Follow-up of AEs and SAEs

 The Investigator is obligated to perform or arrange for the conduct of supplemental measurements and/or evaluations as medically indicated or as requested by Alexion to elucidate

Follow-up of AEs and SAEs

the nature and/or causality of the AE or SAE as fully as possible. This may include additional laboratory tests or investigations, histopathological examinations, or consultation with other health care professionals.

- If a participant dies during participation in the study or during a recognized follow-up period, the Investigator will provide Alexion with a copy of any postmortem findings including histopathology.
- New or updated information will be recorded in the originally completed eCRF.

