- The Investigator will submit any updated SAE data to Alexion within 24 hours of receipt of the information.

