4.5.2. Adverse Events

The following definitions will be used for AEs:

- **Pretreatment AE:** Any AE that starts after providing informed consent, but before the first dose of study intervention (ALXN2050 or placebo)
- Treatment-emergent adverse event (TEAE): Any AE that starts between the start of the first dose of study intervention and up to 30 days after the last dose of study intervention
- Treatment-emergent serious adverse event (TESAE): A TEAE that is serious
- **Post-treatment AEs:** Any AE that starts 30 days or later after the last dose of study intervention

All AEs will be coded using MedDRA version 26.1 or higher and will be summarized by SOC and PT overall, by severity, and by relationship to treatment.

Participants having multiple AEs within a category (eg, overall, SOC, PT) will be counted once in that category. For severity/relationship tables, the participant's highest grade/most related event within a category will be counted.

TEAEs and serious adverse events (SAEs) will be summarized descriptively by treatment group. Percentages will be based on the number of treated participants in the SS within a treatment group. Tables will be sorted by descending frequency of SOC and by descending frequency of PT within an SOC.

Pretreatment and post-treatment AEs will be provided in by-participant listings and will not be included in summary tables.

In addition, AEs that occur after the receipt of additional standard of care therapy will be provided in a separate listing.

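### The TEAE definition rests on AE start date and has no worsening clause, so a Screening-onset AE that worsens or turns serious on study drug may be missing from the TEAE and TESAE tables

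*SAP*

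**What the plan says.** SAP section 4.5.2 defines a TEAE as "Any AE that starts between the start of the first dose of study intervention and up to 30 days" after the last dose. It defines a TESAE as "A TEAE that is serious" and a pretreatment AE as "Any AE that starts after providing informed consent, but before the first dose of study intervention". Section 6.1.7 repeats the start-date rule for TEAEs ("Treatment-emergent AEs (TEAEs) are events with start dates and start times on or after the date and time of the first dose") and assigns any other AE with a pre-dose start to the pretreatment class. Section 4.5.2 then fixes how that class is reported: "Pretreatment and post-treatment AEs will be provided in by-participant listings and will not be included in summary tables".

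Protocol section 8.3.1 collects AEs from consent, and section 4.1.1 allows up to 6 weeks of Screening. Protocol section 10.3.1 includes among the events that count as AEs "Exacerbation of a chronic or intermittent pre-existing condition including either an increase in" frequency or intensity. It also includes clinically significant laboratory or other safety results that have worsened since baseline. On follow-up, Protocol section 10.3.3 says: "New or updated information will be recorded in the originally completed eCRF".

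**The concern.** The incidence of TEAEs and TESAEs is one of the trial's stated safety endpoints (Protocol section 3; SAP section 1.1). An event that was mild in Screening and becomes severe or serious after dosing is a harm that the comparison with placebo should be able to show. Under a rule based on start date, that change does not count unless someone has given it a new start date.

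Such events are plausible in the LN cohort. Under Protocol section 6.5.3.1, participants not yet on induction treatment receive methylprednisolone and begin mycophenolate during Screening or by Day 1, and start oral corticosteroids by Day 2. Some participants already on induction have their mycophenolate increased in the same window. Adverse effects that begin then may still be present when study drug starts.

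**Working it through.** The plan states no figure on this point, so the check is to apply its rules to one case.

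**Case.** An AE with complete dates starts on Day -10 at Grade 1. On Day 20 it reaches Grade 3 or becomes serious.

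1. *Is it collected?* Yes. Collection starts at consent (Protocol 8.3.1).
2. *If the change is entered on the existing record* (as Protocol 10.3.3 suggests for updates), the start date stays at Day -10. That is before the first dose, so SAP 4.5.2 and 6.1.7 both make it a pretreatment AE.
3. *Is it a TESAE?* No. A TESAE must first be a TEAE, so becoming serious on Day 20 changes nothing.
4. *Where does it appear?* It is absent from the TEAE and TESAE counts in the overall summary (SAP 4.5.2.1) and from the tables by SOC and PT, relationship and severity (4.5.2.2 to 4.5.2.4), which are built on TEAEs and TESAEs. It is in the by-participant listings.
5. *If the site instead opens a new record dated Day 20*, the same clinical change is a TEAE, and a TESAE if serious. It then enters all of those tables.

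Steps 2 and 5 differ only in data entry. The protocol uses the term TEAE in its section 9.4.7.1 without a definition that would settle the matter, and no section says which form of entry is required.

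**Comparison within the SAP.** In section 6.1.7, an AE whose start date is completely missing counts as treatment-emergent unless its stop date rules that out. In section 6.1.9, a medication begun before the first dose and stopped after it counts as concomitant. The SAP therefore has a rule for drug records that straddle Day 1 but none for AE records that do.

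**Size of one omission.** Planned LN arms are 30, 10 and 30 (Protocol Table 8). Percentages use treated participants in the arm (SAP 4.5.2). With all 30 treated, one participant is 1/30 = 3.3 percentage points on the affected SOC/PT, severity or TESAE row.

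**Number of omissions.** This cannot be derived. The documents give no rate of Screening-onset AEs, no rate of later worsening, and no indication of how often sites would update rather than re-enter.

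**The case against.** The strongest reply is that worsening often becomes an AE in its own right, with an on-treatment date. Protocol 10.3.1 covers exacerbations of pre-existing conditions and clinically significant results that worsen from baseline. Its list of non-AEs exempts day-to-day fluctuations only where the condition does not worsen. Protocol 9.4.7.2 classes adverse changes in physical examination as AEs. Protocol 8.12.4 has medical history updated up to the first dose, so a Screening-onset condition may be on record as pre-existing. The sentence about the original eCRF is a follow-up instruction; it does not say that a rise in grade is not a new event.

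Much of this stands. A reader might infer that every Screening-onset AE that worsens is left out of every table. The documents do not support that, because these provisions give sites several routes to a new record. They do not require one, they do not clearly cover an acute event that first arose in Screening, and they do not address a change to serious.

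A second reply is that other outputs would show part of the harm: laboratory shifts and liver-enzyme tables (SAP 4.5.3.1), ECG shift to worst on-study result (4.5.3.3), the count of deaths (4.5.2.1), and listings of discontinuations, seizures and meningococcal infections (4.5.2.5). This also stands, but it does not return a worsening infection, for example, to the between-arm AE tables.

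Third, SAP 4.5.2 and Protocol 9.4.7.1 both mention a summary of SAEs without limiting it to treatment-emergent ones. That conflicts with the exclusion of pretreatment AEs from summary tables. It leaves an ambiguity about serious events rather than a solution.

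**Conclusion.** The gap in the definition is real. For AEs with complete dates, treatment-emergent status follows the start date alone, TESAEs inherit the rule, and an on-drug worsening kept on a Screening record is not counted in the TEAE and TESAE tables. Whether a given event is omitted depends on site recording practice, so the right statement is that it may be omitted. Partial and missing dates follow separate default rules.

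The size is unknown. The 3.3 points is the effect of one participant on one row of a 30-participant LN arm, not an expected bias. The row for any TEAE does not change for a participant who has another TEAE. A reader might also infer a similar problem of known size in IgAN. The definition applies there too, but the mechanism of therapy started in Screening does not: IgAN background treatment must be stable for at least 3 months before Screening (inclusion criterion 15) and is to be held stable through Week 50 (Protocol 6.5.3.2).

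Safety analyses are descriptive, with no formal testing (SAP 4.5). The correction is worth making because it concerns a stated endpoint, the arms are small and the change is cheap. It does not put the primary efficacy analysis in doubt.

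**What to change.** In SAP sections 4.5.2 and 6.1.7, add to the TEAE definition: *or an AE that started before the first dose and increases in CTCAE grade or becomes serious on or after the first dose and up to 30 days after the last dose, counted at the worsened grade from the date of worsening.* Exclude such events from the pretreatment class, so that the two sections stay consistent. State whether the SAE summary is limited to treatment-emergent events.

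Instruct sites to record such a worsening either as a new AE record or as a dated change in grade or seriousness. An instruction alone will not repair existing records, because screening, enrollment and dosing were paused from 06 Sep 2024 (SAP section 1). For data already collected, query every AE ongoing at Day 1, before database lock, for any later rise in grade or change to serious and its date.

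The cost is a sentence in two places, an eCRF completion instruction and a limited round of data queries. TEAE counts may rise slightly in all arms.
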